Based on observed rates of QFT positivity 1 year after MTBVAC vaccination in infants, half or more of infants who receive MTBVAC may remain QFT positive at end of study and longer. However, it will not be possible to differentiate MTBVAC-induced QFT conversion from QFT conversion as a consequence of natural *M. tuberculosis* infection. Therefore, risk of natural *M. tuberculosis* infection will be minimized by exclusion of infants with known TB exposure, including prior maternal or family history. Infants who demonstrate QFT conversion soon after

MTBVAC administration are more likely to have converted due to vaccine effect than infants who demonstrate QFT conversion later during follow-up, who are more likely to have converted due to natural *M. tuberculosis* infection. Early (D56) post-vaccination QFT conversion in infants with low risk of natural *M. tuberculosis* exposure is assumed to be vaccine-induced and will not be treated with isoniazid preventive therapy (IPT). Infants who demonstrate early QFT conversion at D56 will undergo enhanced screening for potential new TB exposure and TB symptoms during all scheduled study visits, and in addition, during interval telephonic contacts at D120 and D270. QFT samples will be collected at D182 and D365 from infants who tested QFT positive at D56, and stored for later analysis, but since a positive QFT result would not be interpretable, these data will not be used for clinical decision-making. All infants who received MTBVAC and tested QFT positive will receive a card at the end of study indicating that they have received an experimental vaccine that may interfere with interpretation of future IGRA and TST tests for TB infection.

QFT assays will be repeated at D182 and D365 in infants who tested QFT negative at D56. These results will be made available for clinical decision-making. Infants with new QFT conversion events at D182 or D365, and any infant with a reported new household TB contact regardless of QFT status, will be referred to the public health services for IPT since these infants would potentially benefit from TB prophylaxis against *M. tuberculosis* infection as per SA national guidelines, provided that signs and symptoms of active TB disease are absent.

Known Potential Benefits

All infant participants will benefit from enhanced TB screening and facilitated referral and improved access to healthcare providers.

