- Record any adverse events, including unsolicited adverse events, solicited and unsolicited injection site reactions, and serious adverse events (including concomitant medications).
- 8. Examine site of injection (includes measurement of redness, swelling, and ulceration) and take a pus swab if discharge present.
- 9. Blood collection for:
 - Immunogenicity WB-ICS
 - QuantiFERON®-TB Gold Plus test

Study Day 120 ±7 days and Study Day 270 ±7 days

Home / telephonic visit if infant tested QFT positive at D56 to enquire about TB signs and symptoms and general well-being

Study Day 182

Allowable window for clinic visit is 182 ±14 days from Study Day 0 visit date.

- 1. Verbally reconfirm consent.
- 2. Update medical history including use of medications.
- 3. Screening for potential new TB exposure and TB symptoms.
- 4. Record feeding practice.
- 5. Vital signs (heart rate, respiratory rate, axillary temperature, weight and recumbent length).
- 6. Focused physical examination.
- 7. Record any adverse events, including unsolicited adverse events and serious adverse events (including concomitant medications).
- 8. Examine site of injection (includes measurement of redness, swelling, and ulceration) and take a pus swab if discharge present.
- 9. Blood collection for:
 - Immunogenicity WB-ICS
 - QuantiFERON®-TB Gold Plus

Partial Cohort Unblinding of Data Post Study Day 182

Once the last Cohort 3 Study D182 visit has been completed, an independent biostatistician be unblinded to available study data. At this point Cohort 1 and Cohort 2 participants will have completed all study visits and these participants and clinical team will be unblinded post Study D365 visit. All available safety data for all cohorts up to the last Cohort 3 Study D182 visit completion; and immunogenicity data for all cohorts up to each cohort's Study D182 visit, will be analysed by the independent, unblinded biostatistician and provided to DSMB for review to determine MTBVAC dose selection for the Phase III study. The Sponsor will review blinded data only in order to keep the blind until post Study D365 visit. The DSMB will be provided with the same blinded data along with unblinding vaccine recipient lists. The DSMB review will allow for a blinded recommendation and input into the dose selection for the Phase III study. For all cohorts, unblinding of the clinical team and participants will take place post Study D365 visit.

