9.1.1 Screening for TB and referral for Isoniazid Preventive Therapy

All infants will undergo screening for potential new TB exposure and TB symptoms at each visit and caregivers will be encouraged to report such symptoms or any new household TB contact if they occur in between visits. If TB symptoms or potential new TB exposure are

detected these infants will be investigated for active TB disease and may be referred to the public health clinic for initiation of TB treatment if indicated or IPT if active TB is ruled out.

Early (D56) post-vaccination QFT conversion in infants with low risk of natural *M. tuberculosis* exposure is assumed to be vaccine-induced and will not be treated with isoniazid preventive therapy (IPT). Infants who demonstrate early QFT conversion at D56 will undergo enhanced screening for potential new TB exposure and TB symptoms during all scheduled study visits, and in addition, during interval telephonic contacts at D120 and D270. QFT samples will be collected at D182 and D365 from infants who tested QFT positive at D56, and stored for later analysis, but since a positive QFT result would not be interpretable, these data will not be used for clinical decision-making. All infants who received MTBVAC and tested QFT positive will receive a card at the end of study indicating that they have received an experimental vaccine that may interfere with interpretation of future IGRA and TST tests for TB infection..

QFT assays will be repeated at D182 and D365 in infants who tested QFT negative at D56. These results will be made available for clinical decision-making. Infants with new QFT conversion events at D182 or D365, and any infant with a reported new household TB contact regardless of QFT status, will be referred to the public health services for IPT since these infants would potentially benefit from TB prophylaxis against *M. tuberculosis* infection as per SA national guidelines, provided that signs and symptoms of active TB disease are absent.

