APPENDIX A. SCHEDULE OF EVENTS

		Study day Visit Window (hrs/days)							
Evaluation	Screen	D0	D7	D28	D56	D182	D365	Post D365	Early termination
	NA	+96 hrs	±3d	±3d	±7d	±14d	±14d	NA	NA
Informed consent process	Ma								
Medical history	М								
TB symptoms or household TB contact	М	х	Х	х	х	х	х	х	х
Maternal HIV result available	М								
Verbally reconfirm consent	М	М	М	М	М	M	М	М	
Verify eligibility criteria	Х	Х							
Vital signs, length, weight		Х	Х	х	х	х	Х	Х	X
Record feeding practice		Х	Х	Х	Х	х	х	х	х
Physical examination		Х	Х	Х	Х	х	х	х	х
Recording of concomitant medication		Х	Х	х	Х	х	х	х	х
Randomization		Х							
MTBVAC/BCG administration		Х							
Safety blood sampling (mL) ^b			2						
QuantiFERON®-TB Gold Plus (mL)b					4 ^d	4	4		4
Whole blood (mL) ^b				2	2	4	4		
(12-hour WB-ICS)							7		
Distribute/review diary cards		Х	Х						
Solicited systemic adverse events (incl. concomitant medications)		х	x	х					
Unsolicited adverse events (incl. concomitant medications)		х	x	х	х	х	х		х
Solicited and unsolicited injection site reaction adverse events (incl. concomitant medications)		х	х	х	х				
Serious adverse events (incl. concomitant medications)		х	х	х	х	х	x		x
Site of injection examination swab if discharge		х	Х	х	х	х	х		x
Rescue dose BCG post unblinding of cohort ^c								x	
Approximate per visit phlebotomy volume (mL) ^a			2	2	6	8	8		4
Cumulative phlebotomy volume (mL)b			2	4	10	18	26		NA

^a Maternal - the mother signs once, antenatally, and thereafter reconfirms consent orally at each visit

^b Acceptable infant blood sample volumes in clinical research are limited to <3% of the total blood volume (TBV), and no more than 3mL/kg over an 8 week period

^c Telephonic contact/ home visit approximately 14 days post BCG to confirm infant's wellbeing incl. BCG injection site reaction

^d If QFT positive at D56 a home/telephonic visit will be done at D120±7d and 270±7d to monitor infant's wellbeing, specifically enquiring about TB signs and symptoms

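### Four places in the protocol disagree on whether the D120 and D270 contacts in D56 QFT-positive infants ask about new TB exposure or only about symptoms and well-being

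*Combined protocol and SAP*

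**What the plan says.** Two places give the D120 and D270 contacts two tasks. For infants with early QFT conversion, Section 3.3.1 asks for "screening for potential new TB exposure and TB symptoms during all scheduled study visits, and in addition, during interval telephonic contacts at D120" and D270. Section 9.1.1 repeats the requirement, again placing both tasks "during interval telephonic contacts at D120 and D270".

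Two places give a shorter list. Section 8.3 describes each contact as a "Home / telephonic visit if infant tested QFT positive at D56 to enquire about TB signs and symptoms and general well-being". Footnote d of Appendix A says the contact is "to monitor infant's wellbeing, specifically enquiring about TB signs and symptoms". Appendix A does have a row headed "TB symptoms or household TB contact", but the table has no D120 or D270 column, so footnote d is its only instruction for these contacts.

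On what follows from an exposure, Section 3.3.1 says that "any infant with a reported new household TB contact regardless of QFT status, will be referred to the public health services for IPT", provided signs and symptoms of active TB are absent. The same section says that D56 conversion in infants at low risk of natural exposure is taken as vaccine-induced and not treated, and that D182 and D365 QFT results in D56-positive infants are not used for clinical decisions.

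**The concern.** Sections 8 and 9.1 send the reader to Section 8 and Appendix A for what is done at each visit. Staff preparing a call sheet for D120 or D270 from those places would have no prompt to ask about a new TB contact in the household.

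The contacts exist only for infants who were QFT positive at D56, and these are the infants for whom later QFT results cannot prompt action. A symptom-free infant in this group depends on a household contact being reported. Section 3.3.1 states that protection from MTBVAC relative to BCG is unknown and promises measures to minimise TB risk throughout. A longer interval between exposure questions weakens one of those measures. It also makes the dating of exposures coarser, and that dating has some bearing on the exploratory aim of separating vaccine responses from natural infection.

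**Working it through.** The protocol gives no figure to reproduce. The check is a comparison of text, followed by subtraction of study days.

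**Step 1. Content of the D120 and D270 contacts**

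| Place | Symptoms | New exposure | Well-being |
|---|---|---|---|
| Section 3.3.1 | yes | yes | not listed |
| Section 9.1.1 | yes | yes | not listed |
| Section 8.3 | yes | not listed | yes |
| Appendix A, footnote d | yes | not listed | yes |

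**Step 2. Could symptoms be shorthand for both?** Probably not. The visit lists in Section 8 name exposure and symptoms separately at D0, D7, D28, D56, D182 and D365. The Appendix A row for clinic visits also names household contact as well as symptoms. Where exposure is meant, these parts of the protocol say so.

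**Step 3. Routes to IPT for a D56-positive infant**

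- D56 result: not acted on in low-risk infants (Sections 3.3.1 and 9.1.1).
- D182 and D365 results: samples stored, not used clinically (same sections; Table 9-1, note c).
- TB symptoms: investigated, with possible referral for IPT once active TB is ruled out (Section 9.1.1, permissive wording).
- Reported new household contact: referral stated as definite, if there are no signs or symptoms of active TB.

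For a symptom-free infant, only the last route carries a definite referral.

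**Step 4. Gaps between active exposure questions.** Inputs are the scheduled days and windows in Section 8.3, Section 8.4 and Appendix A: D56 ±7, D120 ±7, D182 ±14, D270 ±7, D365 ±14. The nominal gap is the later day minus the earlier day. The maximum gap is (later day + its window) − (earlier day − its window).

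If exposure is not asked at D120 and D270:

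- D56 to D182: 182 − 56 = 126 days; maximum 196 − 49 = 147.
- D182 to D365: 365 − 182 = 183 days; maximum 379 − 168 = 211.

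If exposure is asked at D120 and D270:

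- D56 to D120: 120 − 56 = 64 days; maximum 127 − 49 = 78.
- D120 to D182: 182 − 120 = 62 days; maximum 196 − 113 = 83.
- D182 to D270: 270 − 182 = 88 days; maximum 277 − 168 = 109.
- D270 to D365: 365 − 270 = 95 days; maximum 379 − 263 = 116.

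The longest nominal gap is therefore 183 days on one reading and 95 on the other, a difference of 183 − 95 = 88 days.

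**The case against.** The best defence is that Section 9.1.1 belongs to the procedures chapter and names exposure at both contacts. It also says that all infants are screened for exposure at each visit, and Section 8.3 and footnote d both call these contacts visits. Nothing in the shorter descriptions excludes exposure. On this view the two shorter entries are incomplete summaries of a procedure set out elsewhere. Caregivers are also encouraged to report a household contact between visits.

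Much of this stands, and it rules out several stronger readings:

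- A reader might infer that exposure screening is unscheduled at D120 and D270. It is scheduled in Sections 3.3.1 and 9.1.1. The fault is disagreement between places.
- A reader might infer that household contact is the only route to IPT in these infants. Section 9.1.1 leaves open referral after symptoms, and symptoms are asked about at these contacts in all four places. The claim holds only for definite referral of a symptom-free infant.
- A reader might infer that recorded exposure is the only individual-level evidence on natural infection. Section 3.3.1 itself relies on the timing of conversion, and the quantitative QFT results (Section 4.2.2) and ICS responses (Section 4.2.1) also bear on it.
- A reader might want a count of infants harmed. An assumed D56 positivity rate would give the number of infants contacted, not the number with a missed exposure. The protocol gives no D56 rate and no incidence of household contact after enrolment.

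The defence does not make the four places agree. Those that Sections 8 and 9.1 name for visit procedures still omit the item, and encouragement to self-report is not the active screening that Section 3.3.1 describes.

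**Conclusion.** The inconsistency is real and lies in the current text. Its size is the difference in active enquiry: nominal gaps of 126 and 183 days if the site follows Section 8.3 and Appendix A alone, against at most 95 days under Sections 3.3.1 and 9.1.1. This assumes that staff take the content of the contacts from the visit schedule and that the caregiver does not report a contact unprompted. If either assumption fails, the longer gap does not arise for that infant. The form or script used at these contacts is not in the documents, so it may already include the question.

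This is a matter of participant follow-up in a group whose QFT results cannot guide care. It touches no primary or secondary endpoint and no planned analysis. It is worth correcting because the change is small and the infants concerned have few other prompts for referral.

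**What to change.** Reconcile Section 3.3.1, Section 8.3, Section 9.1.1 and footnote d of Appendix A so that all four state the same content for the D120 and D270 contacts, and make the form used at those contacts match. Which content is intended is for the sponsor and the investigator to decide; this point asks only that it be stated once and consistently.

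The cost is a text edit and a check of one form, with no extra visit and no extra blood. As a protocol change it would follow the approval route in Section 15.1, so it could travel with another amendment.

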4 OBJECTIVES

4.1 Study Objectives

Primary Objectives

The primary objectives of this study are:

- To evaluate safety and reactogenicity of MTBVAC at escalating dose levels compared to BCG vaccine in healthy, BCG naïve, HIV unexposed, South African newborns.
- To evaluate the immunogenicity of MTBVAC at escalating dose levels compared to BCG vaccine in healthy, BCG naïve, HIV unexposed, South African newborns.

Secondary Objective

The secondary objective of this study is:

 To evaluate QFT conversion rates in neonates receiving escalating dose levels of MTBVAC.

Future Exploratory Objective

Samples will be kept for future analyses:

- To evaluate exploratory immune responses to escalating dose levels of MTBVAC and to BCG (including, but not necessarily limited to, analysis of innate response cytokines, specific IgG antibody responses, donor-unrestricted T-cell responses).
- To differentiate vaccine-induced immune responses from natural Mtb infection

4.2 Study Outcome Measures

4.2.1 Primary Outcome Measures

The primary outcome measures are:

Safety and reactogenicity endpoints:

- Solicited systemic adverse events: fever, irritability, vomiting, diarrhea, drowsiness, poor feeding, skin rash.
- Solicited injection site reaction adverse events: pain, redness, swelling, ulceration, drainage, and regional lymphadenopathy
- Unsolicited adverse events and serious adverse events

Immunogenicity endpoints:

• Frequencies of antigen-specific IFN-γ, TNF-α, IL-2, IL-17 and/or IL-22-expressing CD4 and CD8 T cells measured by 12-hour whole blood (WB) intracellular cytokine staining (ICS) assay at Study Days 28, 56, 182, and 365. Stimulating agents at Study Days 28 and 56 will include MTBVAC, ESAT-6, CFP-10, EspC and a "megapool" of peptides containing immunodominant *M. tuberculosis* epitopes (16). Stimulating agents at Study Days 182 and 365 will include MTBVAC, ESAT-6, CFP-10, EspC and a "megapool" of peptides containing immunodominant *M. tuberculosis* epitopes (16) as well as a modified version of the "megapool" but containing only those epitopes shared by both BCG and MTBVAC.

4.2.2 Secondary Outcome Measures

The secondary outcome measures are:

 Quantitative and qualitative results of the QFT Gold Plus assay at Study Day 56, 182 and 365.

[figure not shown]
5 STUDY DESIGN

This double-blind, randomized, active controlled, MTBVAC dose-finding trial will evaluate the safety, reactogenicity, immunogenicity, and potential for QFT conversion and reversion of the candidate TB vaccine MTBVAC in HIV uninfected BCG naïve newborns, administered in 3 cohorts at a single intradermal dose of 2.5×10^4 CFU (Cohort 1, n=25), 2.5×10^5 CFU (Cohort 2, n=25), and either 2.5×10^6 CFU (n=25) or 2.5×10^5 CFU (n=13) plus 2.5×10^4 CFU (n=12) (Cohort 3), compared to BCG vaccine (24 BCG; 75 MTBVAC).

Three dose levels of MTBVAC (2.5 x 10³, 2.5 x 10⁴, 2.5 x 10⁵ CFU) have been tested in the current Phase 1b trial in healthy, BCG-naïve, South African newborns; and four dose levels (5 \times 10³, 5 x 10⁴, 5 x10⁵, and 5 x 10⁶ CFU) are being tested in a parallel trial among M. tuberculosis infected and uninfected South African adults. It is our hypothesis that the optimal safe and immunogenic MTBVAC dose for infants lies in the range of 2.5 x 104 (10-fold lower than BCG) to 2.5 x 10⁶ CFU (10-fold higher than BCG). Therefore, this proposed infant trial aims to define the MTBVAC dose-response curve above and below the optimal MTBVAC dose, straddling a 3-log dose range. Final selection of the MTBVAC dose for use in the 3rd cohort will be data driven, based upon the most recent safety and immunogenicity data from all ongoing and completed trials of MTBVAC in infants and adults at that time. Infant safety data are not yet available for the highest (2.5 x 10⁶ CFU) MTBVAC dose. Therefore, selection of the 2.5 x 106 CFU MTBVAC dose would be contingent upon demonstration of an acceptable safety profile (as defined in Section 3.3.1), both for all lower MTBVAC doses in infants, and for the 5 x 10⁶ CFU MTBVAC dose in QFT negative adults (data expected end 2018/beginning 2019). If these safety criteria for the highest MTBVAC dose are not fulfilled, the 2.5 x 10⁵ CFU and 2.5 x 104 CFU MTBVAC doses would be selected for the last cohort, as described in Section 3.3.1. This approach will build upon data from the current infant pilot study and should allow detailed comparison of safety and immunogenicity of the postulated optimal MTBVAC dose within a 3-log dose range, in a larger infant study population. Refer to Figure 5-1.

In addition, given the crucial importance of understanding the immunological basis for MTBVAC vaccine-induced QFT conversion, and defining the time course and magnitude (IFN-g concentration) of MTBVAC vaccine-induced QFT conversion and reversion events, serial QFT assays will be performed in parallel with whole blood T cell assays.

Figure 5-1 Study Flow Diagram

¹ Cohort 1: n=25 MTBVAC (2.5 x 104 CFU) and n=8 BCG

² Cohort 2: n=25 MTBVAC (2.5 x 10⁵ CFU) and n=8 BCG

³ Cohort 3: n=25 MTBVAC (2.5 x 106 CFU OR 2.5 x 105 CFU (n=13) plus 2.5 x 104 CFU (n=12)) and n=8 BCG

⁴ At each DSMB, all available safety data from previous cohorts enrolled will be reviewed. If any of the safety criteria is not met for the 2.5 x 10° CFU dose for Cohort 3, Cohorts 1 and 2 will be expanded so that 33 additional neonates will be randomly allocated to receive the 2.5 x 10° CFU dose (n=13), the 2.5 x 10° CFU dose (n=12) or BCG (n=8) by default.

6 STUDY ENROLLMENT AND WITHDRAWAL

6.1 Participant Inclusion Criteria

Participants must meet all of the following criteria at the time of randomization:

- 1. Male or female neonates within 96 hours of birth.
- 2. Written informed maternal consent, including permission to access maternal antenatal, postnatal and infant medical records.
- 3. Infant participants and their caregivers available for study follow-up and display the willingness and capacity to comply with study procedures.
- 4. Neonates must be in good general health during pregnancy and delivery, as assessed by medical history and focused physical examination.
- 5. Birth weight ≥ 2450 grams.
- 6. Appar score at 5 minutes \geq 7.
- 7. A maternal HIV test result (rapid test, ELISA or PCR) taken within 30 days of delivery must be available, documented and negative.
- 8. Estimated gestational age ≥ 37 weeks.
- Mother has not participated in a clinical trial within 3 months prior to the infant's birth, and
 if breast-feeding, mother should not participate in a clinical trial during the 12 months of
 study follow up.
- 10. Mother has never participated in a TB vaccine trial before.
- 11. Infant may not participate in any other clinical trial from birth, and for the 12 months of follow up.

6.2 Participant Exclusion Criteria

Participants must have none of the following at the time of randomization:

- 1. Participant must not have received BCG vaccination prior to enrolment.
- 2. Significant antenatal or intrapartum complications that may affect the health of the neonate.
- 3. Skin condition, bruising or birth mark at the intended injection site.
- 4. Maternal HIV test (rapid test, ELISA or PCR) not performed within 30 days of delivery, HIV test results not available, or HIV test result known positive.
- 5. History of close contact with a TB patient, antenatal or postnatal, whether maternal, other family member or another household member who has not yet completed TB treatment.
- Clinically suspected neonatal sepsis.
- 7. Any severe congenital malformation.
- 8. History or evidence of any systemic disease on examination, or any illness that in the opinion of the investigator may interfere with the evaluation of the safety and immunogenicity of the vaccine. Neonatal jaundice not considered clinically significant is not an exclusion.

